#### 4.6.2 Rationale for sequencing for stereotactic radiation surgery and pembrolizumab

To date, no studies have reported on the efficacy of SRS and anti-PD1 checkpoint inhibitor, pembrolizumab. Three published pre-clinical studies have investigated combining radiation therapy and anti-PD1 in mouse models. While they show a synergistic

relationship between the two therapies, these studies did not investigate the ideal sequencing of the two proposed therapies (anti-PD1 and SRS). While evidence for sequencing is therefore missing, the Memorial Sloan Kettering group retrospectively reported on the safety and efficacy of 46 patients treated with SRS and CTLA-4 checkpoint inhibitor, ipilimumab. 15 patients received SRS during ipilimumab, 19 received SRS before IPI and 12 received SRS after IPI. Grade 3 or higher toxicities was 20% in the entire cohort, consistent with rates of grade 3 toxicities with ipilimumab alone. Grade 3 or higher CNS adverse effects included seizure (4.6%) and CNS bleeding (10.9%). Rate of toxicities did not correlate with sequence of therapies; these findings are also consistent with our own institutional series as well as others.

Overall survival was higher in the cohort that received SRS before or during IPI, than those treated with SRS after ipilimumab. However, an inherent selection bias may account for these findings, as patients in the SRS after IPI cohort may be selected for SRS due for salvage after ipilimumab alone. Interestingly, the authors did find that 50% of patients treated with SRS before or during IPI had an increase in size > 150%, compared to 15% with those treated with SRS after IPI. They hypothesized that this increase in size represents T cell infiltration of the tumor, thereby demonstrating potential activity. Because (1) sequence did not correlate with toxicity, (2) but did correlate with possible activity, and (3) preclinical research suggests concurrent radiation and anti-PD-1 therapy is synergistic, we will plan to utilize the approach of concurrent SRS with the checkpoint inhibitor pembrolizumab.

We suspect that the maximum T cell activation, proliferation, and entry into the blood stream occurs within 48 hours. To maximize the exposure of these cells to the increased antigen expression and MHC levels, we will plan to deliver radiation with 24 to 48 hours after pembrolizumab is delivered (and no later than 7 days after the first PD-1 inhibitor infusion).

#### **4.6.3 Rationale for Primary Endpoint**

For intact brain metastases treated with SRS alone, Aoyama demonstrated prospectively that 8 out of 67 patients (12%) developed an acute grade 3 CNS toxicity. RTOG 90-05 accepted a 20% acute grade 3 CNS toxicity in their trial design. Similar rates were observed in the cohort treated with SRS alone on the Kocher prospective study. For large lesions, we and others have retrospectively demonstrated a grade 2 toxicity rate of 10% for hypofractionation. For pembrolizumab alone, acute grade 3 nervous system toxicity was seen in 2 out of 18 patients (11%). Therefore, assuming toxicity is additive, we will accept a DLT toxicity rate of 25%, with a 5% room for error. Thus, our acceptable DLT is 33%. This rate is justified given that (1) each therapy alone (SRS and anti PD-1 alone) have limitations as detailed above and (2) the combination may result in significantly higher response and perhaps improved outcomes in combination.

## 5.0 ENROLLMENT CRITERIA

### 5.1.1 Subject Inclusion Criteria

In order to be eligible for participation in this trial, the subject must:

1. Be willing and able to provide written informed consent/assent for the trial.
2. Be  $\geq 18$  years of age on the day of signing informed consent.
3. ECOG PS of 0-1 (See Appendix IV for ECOG definition); Karnofsky Performance Status  $\geq 70\%$ ;
4. Patients must have histological diagnosis of melanoma or non-small cell lung cancer (biopsy will be done per standard of care, if needed to prove metastatic melanoma and/or NSCL as well as for clinically relevant mutation analysis); Additional biopsy will be per standard of care.
5. Patients can be treated either in first line or in the refractory setting; PD-L1 positivity is not required for enrollment;
6. All melanoma patients may be tested for BRAF as part of routine standard of care, but is not a requirement for the trial; All NSCLC patients may be tested for with EGFR and ALK as part of standard of care, but is not a requirement of the trial.
7. Having gotten prior PD1 therapy is allowed for, especially if they have previously progressed on it. Progression may include extra-cranial as well as intra-cranial progression. After progressing on PD1 therapy, intervening chemotherapy and/or targeted therapy (BRAFi, etc) is allowed. If they are on intervening chemotherapy and/or targeted therapy (BRAFi, etc), they have to have progression intra-cranially and/or extra-cranially and must be off intervening therapy for at least 2 weeks.
8. Patient must be asymptomatic at time of getting SRS (day 0) on trial. Prednisone  $\leq 10\text{mg/day}$  for at least 7 days prior to treatment is allowed.
9. Patients with ocular, mucosal and unknown primary melanoma will also be eligible
10. Patients with 1-10 untreated brain metastases at time of initial brain metastases diagnosis (surgery to one of the brain lesions and/or biopsy of a lesion for diagnostic purposes and/or for standard of care purposes is acceptable).
11. Largest brain metastases volume measures less than  $14.15\text{cc}^3$
12. Prior radiation to the primary and/or regional radiotherapy for melanoma and/or NSCLC is acceptable.
13. Baseline labs as within standard of care (CBC, CMP, LDH, ESR, etc) are required within 14 days of enrollment
14. Have measurable disease based on RECIST 1.1.
15. Patients must have at least 14 days to recover from all prior treatment, including surgery, chemotherapy, immunotherapies, prior to enrollment on this protocol.
16. Demonstrate adequate organ function as defined in **Table 4**, all screening labs should be performed within 14 days of treatment initiation.

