**Table 1 – Radiation Dose Arms**

Group	Dose per fraction (Gy)	Number of Fractions	Acute BED	Chronic BED
A	6	5	48	90
B	9	3	51.3	108
C. tumor volume < 4cm 	21	1	65.1	168
tumor volume 4-14.15 cm 	18	1	50.4	128

BED = biological equivalent dose. Acute BED is the biological equivalent dose for acute radiation responding tissue, which includes malignant cells. Chronic BED biological is the biologic equivalent dose for late radiation responding tissue, which includes normal brain tissue. Increasing chronic BED doses predicts higher risk of sub-acute and chronic toxicities.

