#### 4.0.2 Stereotactic Radiation Surgery for Brain Metastasis

Historically, most traditional cytotoxic chemotherapies have a limited role in brain metastasis, in part due to blood brain barrier (BBB) limiting penetration. As a result, the standard of care for brain metastasis includes surgery and/or radiation therapy. Although very effective for symptomatic control, Kocher et al. demonstrated that surgical resection alone commonly results in high local failure of 59% at 2 years. To improve local control (LC) and distant brain control (DBC), adjuvant whole brain radiation therapy (WBRT) has been utilized.

With concern, for late neurocognitive toxicities from irradiating the whole brain, more conformal radiation treatments have been developed. Stereotactic radiation therapy (SRS) is a technique that focuses high doses of radiation therapy to the tumor while minimizing radiation therapy to the rest of the brain. Although SRS has lower rates of distant intracranial control for non-targeted subclinical disease, a prospective study has illustrated that SRS alone has similar survival rates to WBRT alone. Furthermore, the addition of WBRT to SRS for patients with 1—3 brain metastases did not improve OS. Retrospective analyses in the post-operative setting have also demonstrated SRS has similar LC and OS to WBRT after controlling for the number of brain metastases.

We at Emory have adopted this approach to treat brain metastasis, including melanoma and NSCLC, with SRS alone to delay WBRT and its related neurocognitive sequelae. Our contemporary analysis supports this regimen for brain metastasis patients: directly comparing post-operative SRS to WBRT, we found (Patel et al) both radiation treatments offer similar local control and median survival, but SRS in 80% of patients prevented the need for WBRT at 1 year. In the intact brain metastases setting, we at Emory have illustrated (Prabhu et al) that 1 year local control rate with SRS was 82%. The local control rate is comparable to other similar published series utilizing radiosurgery. Our studies contribute to the body of evidence that SRS can help improve local intracranial control.

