### 5.1.2 Subject Exclusion Criteria

The subject must be excluded from participating in the trial if the subject:

1. Has a diagnosis of immunodeficiency or is receiving systemic steroids (less than or equal to 10 mg prednisone equivalent at time of start of treatment is ok) therapy or any other form of immunosuppressive therapy within 7 days prior to the first dose of trial treatment
2. If they have brain metastases located in the brain stem (including midbrain, pons, or medulla);
3. Inability to undergo MRI evaluation for treatment planning and follow-up
4. Is currently participating and receiving study therapy or has participated in a study of an investigational agent and received study therapy or used an investigational device within 4 weeks of the first dose of treatment. Has a diagnosis of immunodeficiency or is receiving systemic steroids (less than or equal to 10 mg prednisone equivalent at time of start of treatment is ok) therapy or any other form of immunosuppressive therapy within 7 days prior to the first dose of trial treatment.
5. Has a known history of active TB (Bacillus Tuberculosis)
6. Hypersensitivity to pembrolizumab or any of its recipients.
7. Has had prior chemotherapy, targeted small molecule therapy, or radiation therapy within 2 weeks prior to study Day 1 or who has not recovered (i.e.,  $\leq$  Grade 1 or at baseline) from adverse events due to a previously administered agent.
  - Note: Subjects with  $\leq$  Grade 2 neuropathy are an exception to this criterion and may qualify for the study.
  - Note: If subject received major surgery, they must have recovered adequately from the toxicity and/or complications from the intervention prior to starting therapy.
8. Has a known additional malignancy that is progressing or requires active treatment. Exceptions include basal cell carcinoma of the skin or squamous cell carcinoma of the skin that has undergone potentially curative therapy or in situ cervical cancer.
9. Has active autoimmune disease that has required systemic treatment in the past 2 years (i.e. with use of disease modifying agents, corticosteroids or immunosuppressive drugs). Replacement therapy (eg., thyroxine, insulin, or physiologic corticosteroid replacement therapy for adrenal or pituitary insufficiency, etc.) is not considered a form of systemic treatment.

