**11.1.9 Dose Limitation to Critical Structures**

1. In addition to the above defined GTVs, CTVs and PTVs, both eyes, the lenses of both eyes, the optic nerves, the optic chiasm, cochlea, the brainstem, and the spinal must be evaluated per standard of care approaches. Dose-volume histograms will be generated and whole organ dose and maximum point dose will be recorded for each critical structure. Dose limitations to normal structures are defined in **Table 9**.

2. If the patient has received no prior cranial irradiation, the maximal point doses permissible to the structures from the current radiation therapy plan are listed below.

3. Patient cannot have received whole brain radiation or SRS prior to being enrolled on this trial. However, once on the trial, patient can have received multiple SRS and or whole brain radiation as part of the standard of care treatments for progressive disease; If the patient has received previous brain radiation therapy (while on the trial), the previous dose received to critical structures should be obtained or a representative dose distribution file should be simulated. This dose should then be converted to BED (assuming an alpha-beta ratio of 3 for late effects) and added to the BED to the critical structures from the current treatment plan. This sum BED must meet the cumulative dose constraint below. No adjustments for time between previous radiation treatment will be made for the purpose of this protocol.

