## **APPENDIX VII**

### **Eligibility Checklist**

1. \_\_\_\_\_ Willing and able to provide consent;
2. \_\_\_\_\_  $\geq 18$  yrs old on day of consent;
3. \_\_\_\_\_ Pathological proven diagnosis of one of the following:  
non-small cell lung cancer or melanoma. (biopsy per SOC, if needed)  
Ocular melanoma, mucosal melanoma, and unknown melanoma are eligible;
4. \_\_\_\_\_ Patients can be treated either in first line or in the refractory setting, as long as they can get PD-1 as standard of care; PD-L1 positivity is not required for enrollment;
5. \_\_\_\_\_ 1-10 intact brain metastasis (having had surgery to one lesion is not an exclusion criteria).
6. \_\_\_\_\_ Largest lesion  $\leq 14.15\text{cm}^3$
7. \_\_\_\_\_ Prior whole brain radiation therapy or SRS is allowed  
\*Previous history of radiation to the primary tumor site is eligible;
8. \_\_\_\_\_ Having gotten prior PD1 therapy is allowed for, especially if they have previously progressed on it. Progression may include extra-cranial as well as intra-cranial progression. After progressing on PD1 therapy, intervening chemotherapy and/or targeted therapy (BRAFi, etc) is allowed. If they are on intervening chemotherapy and/or targeted therapy (BRAFi, etc), they have to have progression intra-cranially and/or extra-cranially and must be off intervening therapy for at least 2 weeks.
9. \_\_\_\_\_ Patient asymptomatic at time of SRS (day 0). Use of 10 mg prednisone equivalent at time of start of treatment is permitted as long as the dose has been less than or equal to 10mg for at least 7 days prior to treatment start.
10. \_\_\_\_\_ MRI of brain within 28 +/- 2 weeks days of enrollment showing evidence of BM
11. \_\_\_\_\_ Baseline pre-enrollment CT chest/abdomen/pelvis and/or PET/CT.  
\* Baseline MRI images of chest/abdomen/pelvis can substitute  
\* Baseline bone scan can also be substituted;  
(all imaging must be completed within 28 +/- 2 weeks days of enrollment)
12. \_\_\_\_\_ Photographs of any skin metastases are encouraged, but not required.

13. \_\_\_\_\_ Baseline labs (CBC, CMP, LDH, ESR, etc); collected within 14 days of enrollment
14. \_\_\_\_\_ Measurable disease based on RECIST 1.1;
15. \_\_\_\_\_ ECOG performance status 0-1 and Karnofsky Performance Status  $\geq$  70% on initial visit; Subsequent visits need to only document ECOG PS;
16. \_\_\_\_\_ No concurrent chemotherapy (no chemotherapy starting 14 days before start of radiation to 14 days after completion of radiation).

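### Section 11.1.9 bars whole brain radiation or SRS before enrolment, the Appendix VII checklist allows it, and section 5.1 leans toward the bar without stating it

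*Combined protocol and SAP*

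**What the plan says.** Two places in the current text address brain radiation before enrolment directly.

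- Section 11.1.9, item 3 (dose limits to critical structures): "Patient cannot have received whole brain radiation or SRS prior to being enrolled on this trial".
- Appendix VII, Eligibility Checklist, item 7: "Prior whole brain radiation therapy or SRS is allowed".

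Section 5.1, where eligibility is defined, touches the question only indirectly.

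- Inclusion 10: "Patients with 1-10 untreated brain metastases at time of initial brain metastases diagnosis". A parenthesis then accepts surgery to one lesion, or biopsy. Radiation is not mentioned.
- Inclusion 12: "Prior radiation to the primary and/or regional radiotherapy for melanoma and/or NSCLC is acceptable". The brain is not mentioned.
- Inclusion 15 requires at least 14 days of recovery from earlier treatment.
- Exclusion 7 bars "radiation therapy within 2 weeks prior to study Day 1", with no site named.
- Exclusion 12 lets the investigator exclude a patient whose past therapy might confound the results.

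The primary endpoint is grade 3 or higher RTOG CNS toxicity at 3 months. Under sections 2.3 and 14.1.1, an arm stops if 3 or more of its first 6 patients have it.

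**The concern.** The same patient is ineligible under one section and eligible under another, and the permissive line is in the checklist, the form a site would naturally use at enrolment. The only explicit bar is in a radiation-planning section.

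Patients with earlier brain radiation are plausible candidates. Inclusion 5 says "Patients can be treated either in first line or in the refractory setting", inclusion 7 admits patients who progressed in the brain on earlier therapy, and section 4.0.2 describes the site's practice as "to treat brain metastasis, including melanoma and NSCLC, with SRS alone to delay WBRT".

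What is at stake is the reading of the safety data. The arms fill one after another (section 2.2), with no randomisation or stratification (sections 6.2 and 6.3), so nothing balances earlier brain radiation between them. Section 14.3.1 reports a single toxicity proportion per arm. Section 2.3 chooses the best arm partly on dose-limiting toxicity and radiation necrosis. The note to Table 1 says "Increasing chronic BED doses predicts higher risk of sub-acute and chronic toxicities", which bears most directly on necrosis. Section 14.3.4 censors intracranial outcomes at salvage whole brain radiation but has no rule for whole brain radiation given before entry.

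**Working it through.** **The texts side by side.** Take a patient who had SRS or whole brain radiation three weeks before day 1 and has recovered.

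| Rule | Result |
|---|---|
| 11.1.9 item 3 | Ineligible |
| Appendix VII item 7 | Eligible |
| Inclusion 10 | Unclear. Read literally, lesion status is judged at first diagnosis; the parenthesis suggests no treatment other than surgery or biopsy |
| Inclusion 12 | Silent on the brain; leans toward the bar by listing only other sites |
| Inclusion 15, exclusion 7 | Passes (21 days exceeds 14) |
| Exclusion 12 | Investigator's discretion |

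Section 5.1 leans toward 11.1.9 and checklist item 7 is the outlier, but no line in 5.1 states the bar. The previous-radiation column of Table 9 does not settle it, because 11.1.9 item 3 ties that column to brain radiation received during the trial. The contradiction rests on no number.

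**Illustration 1: chance of stopping an arm.** The plan gives no operating characteristics to reproduce. Base rates come from section 4.6.3: 25% (accepted rate for the combination) and 12% (8 of 67 with SRS alone). Two assumptions are not in the documents: that 2 of 6 patients had earlier brain radiation, and that their DLT rate q is 33% to 50%.

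Uniform rate: P(3 or more of 6) = 1 − Σ C(6,k) p^k (1−p)^(6−k), k = 0 to 2. At p = 0.25 this is 0.169; at p = 0.12 it is 0.026.

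Mixed cohort, with X the DLT count among the other four patients: P = P(X≥3) + P(X=2)[1 − (1−q)²] + P(X=1)q².

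- Base 0.25: P(X=1) = 0.4219, P(X=2) = 0.2109, P(X≥3) = 0.0508.
  - q = 0.33: 0.0508 + 0.2109 × 0.5511 + 0.4219 × 0.1089 = 0.213.
  - q = 0.50: 0.0508 + 0.2109 × 0.75 + 0.4219 × 0.25 = 0.314.
- Base 0.12: P(X=1) = 0.3271, P(X=2) = 0.0669, P(X≥3) = 0.0063.
  - q = 0.33: 0.079.
  - q = 0.50: 0.138.

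With one such patient instead of two, the 25% base gives 0.191 to 0.235.

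**Illustration 2: chronic BED.** BED = n·d·(1 + d/3). This reproduces Table 1 for Arm A (5 × 6 × 3 = 90), Arm B (3 × 9 × 4 = 108) and Arm C at 21 Gy (21 × 8 = 168). The documents give no whole brain schedule. Assume 30 Gy in 10 fractions (10 × 3 × 2 = 60), with a range from 20 Gy in 5 (46.7) to 37.5 Gy in 15 (68.75). Simple addition gives:

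| Arm | Table 1 | Plus 60 | Range |
|---|---|---|---|
| A | 90 | 150 | 136.7 to 158.8 |
| B | 108 | 168 | 154.7 to 176.8 |
| C, 21 Gy | 168 | 228 | 214.7 to 236.8 |

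On these assumptions, an Arm B patient with earlier whole brain radiation matches the chronic BED of an Arm C 21 Gy patient without it.

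**The case against.** The strongest reply is that section 5.1 already points to the right answer. If inclusion 10 asked only whether lesions were untreated when first found, almost any lesion would qualify and its exception for surgery or biopsy would do little. Inclusion 12 permits only non-brain radiation, and exclusion 12 lets the investigator turn away a confounded patient. On that view the checklist line is a slip. Much of this stands: 5.1 does lean toward the bar, and a reader who concluded that it admits these patients outright would go too far. But an implication and a discretionary clause do not override a checklist line that expressly permits them.

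The numbers also invite stronger readings that the documents do not support.

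- A reader might take the BED sums as the protocol's own method. Section 11.1.9 directs summation only for critical structures and only for brain radiation received during the trial. The sums here are a construct for scale.
- A reader might infer that Table 1 proves a higher DLT count. Its note concerns sub-acute and chronic effects, whereas the DLT is an acute toxicity persisting at 3 months. Late necrosis does not stop an arm.
- A reader might say the dose ordering of the arms is lost. That holds only when a previously irradiated patient in one arm is compared with an unirradiated patient in another; with equal earlier dose the ordering remains.

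**Conclusion.** The point holds as an explicit contradiction in current text on an eligibility rule that could plausibly affect the primary safety endpoint. It should be corrected. Confidence in the contradiction is high, and it depends on none of the assumed inputs.

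The size of the effect is unknown. The documents do not give the number of patients with earlier brain radiation, their DLT rate or their earlier dose. The movement from 16.9% to between 21.3% and 31.4% (or from 2.6% to between 7.9% and 13.8%) shows how sensitive a six-patient rule is to two such patients; it does not measure what happened. Nor do the documents show that any such patient was enrolled.

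**What to change.** Follow section 11.1.9 and state the rule where eligibility is decided.

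- Add to 5.1.2: *Has received whole brain radiation or SRS to the brain before enrollment.*
- Change Appendix VII item 7 to: *No prior whole brain radiation or SRS; prior radiation to the primary tumor site is eligible.*
- For any patients already enrolled with earlier brain radiation, report DLTs and radiation necrosis per arm with and without them. Section 13.1.1.6.2 already calls for review of prior radiation, so no new procedure is needed.

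Inclusion 10 need not be reworded to remove the contradiction, and tying its lesion count to a later scan would change when that count is judged.

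The cost is two lines of text and a somewhat smaller eligible pool, of a size the documents do not give. A reader might infer accrual slack from the Trial Summary, since 20 + 27 + 14 + 26 = 87 SRS patients and 45% of 87 is about 39 against 30 needed. That inference is unsafe: the summary itself says 45% yields around 30, and the 87 are all SRS patients, before the other eligibility limits are applied.

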**Table 4 - Adequate Organ Function Laboratory Values**

System	Laboratory Value
Hematological	

Absolute neutrophil count (ANC)	≥1,500 /mcL
Platelets	≥100,000 / mcL
Hemoglobin	≥9 g/dL or ≥5.6 mmol/L without transfusion or EPO dependency (within 7 days of assessment)
Renal	
Serum creatinine OR Measured or calculated a creatinine clearance (GFR can also be used in place of creatinine or CrCl)	≤1.5 X upper limit of normal (ULN) OR  ≥60 mL/min for subject with creatinine levels > 1.5 X institutional ULN
Hepatic	
Serum total bilirubin	≤ 1.5 X ULN OR  Direct bilirubin ≤ ULN for subjects with total bilirubin levels > 1.5 ULN
AST (SGOT) and ALT (SGPT)	≤ 2.5 X ULN OR ≤ 5 X ULN for subjects with liver metastases
Albumin	≥2.5 mg/dL
Coagulation	
International Normalized Ratio (INR) or Prothrombin Time (PT)	≤1.5 X ULN unless subject is receiving anticoagulant therapy as long as PT or PTT is within therapeutic range of intended use of anticoagulants
Activated Partial Thromboplastin Time (aPTT)	≤1.5 X ULN unless subject is receiving anticoagulant therapy as long as PT or PTT is within therapeutic range of intended use of anticoagulants
a Creatinine clearance should be calculated per institutional standard.	

17. Female subject of childbearing potential should have a negative urine or serum pregnancy within 2 weeks prior to receiving the first dose of study medication. If the urine test is positive or cannot be confirmed as negative, a serum pregnancy test will be required.
- a. Female subjects of childbearing potential should be willing to use 2 methods of birth control or be surgically sterile, or abstain from heterosexual activity for the course of the study through 120 days after the last dose of study medication (Reference Section 10.1.2). Subjects of childbearing potential are those who have not been surgically sterilized or have not been free from menses for > 1 year.
  - b. Male subjects should agree to use an adequate method of contraception starting with the first dose of study therapy through 120 days after the last dose of study therapy.
  - c. Abstinence is acceptable, if this is the usual life style and preferred contraception for the patient.

